7.4 Measures taken to avoid bias

In the COPTIC Study, the study population is as representative as possible of the reference cardiac surgery population due to consecutive patients who satisfy the pre-specified inclusion criteria being invited to take part and all who consent are recruited. Analyses have been described (see [section 3.4](#)) to characterise the subgroups of patients who were, and were not recruited. Laboratory analyses of coagulation factor and platelet function are performed in a laboratory that is separate from the site of clinical care of the study subjects and are performed for all patients recruited to the study. Laboratory test results are not made available to the clinicians responsible for direct patient care and would therefore not influence the clinical management of participants. All laboratory tests are performed in a blinded fashion, with the Biomedical Scientists being unaware of all clinical patient data that would identify whether they would be classified as having CCB.

As the post-operative samples are collected earlier in the working day, it is anticipated that laboratory analyses would be performed on the vast majority of samples.

Baseline (i.e. patient demography and past history) characteristics will be described for the eligible and consented patients and for the subcohort of patients available for analysis ([Tables T3 to T4](#)).

Continuous variables will be summarised using the mean and standard deviation (SD) (or median and inter quartile range (IQR) if the distribution is skewed), and categorical data will be summarised as a number and percentages ([Tables T5 to T6](#)).

In order to assess the representativeness of the final analysis populations, the characteristics of those patients included in the analyses will be compared with those not included using data extracted from the PATS Database. All possible demographic factors will be considered. [Table T5 to T6](#) represent what we expect to use to display differences and similarities between those included and those not included in analysis populations.

7.4.1 Descriptive analyses

Distributions of laboratory test results will be described graphically using histograms and density plots.

7.4.2 Adjustment in models

The intention is to adjust all models for potential confounders (see [section 2.7](#))⁷. These will be identified as either by significantly contributing to multivariate models, with likelihood ratio p-value of <0.05, or by modifying the effect estimate by greater than 10%. Age and sex will be entered in all final models, regardless of individual statistical contribution.

Evidence of effect modification will be investigated, by fitting interaction terms into the statistical models and consideration of the effect on the fitted estimates.

7.4.3 Analysis models

All outcomes listed in the study protocol will be presented as per the template tables [Table T7 to T8](#). General methods of presentation are outlined below.

⁷ i.e. factors associated with the both the laboratory test result(s) (exposure) and the outcome, unbalanced across the groups and not an intermediary step in the causal pathway from the exposure to outcome

The primary outcome (CCB) and secondary outcomes (any RBC transfusions > 4 units RBC transfusion, non-routine pro-haemostatic treatments, death, MI, any stroke, renal failure, AKI and infections during hospital admission) are all binary data.

These binary outcomes will be presented as numbers and percentages of patients. The association between laboratory test results and outcome will be quantified using logistic regression for binary data. Estimates will be presented as unadjusted and adjusted odds ratios (OR) and 95% confidence intervals (95% CI). For these binary outcomes analyses will only be performed if more than ten patients in total experience the outcome.

The sensitivity and specificity of laboratory test results to predict the outcome will be described for different thresholds and laboratory tests will be compared using the area under the receiver operating characteristic (ROC) curve.

The association between time of withdrawal of P2Y₁₂ blocker and laboratory test results will be described using linear regression.

7.4.4 Statistical significance

For hypothesis tests and tests of interactions, two-tailed p-values < 0.05 are considered statistically significant. Likelihood ratio tests will be used in preference to Wald tests for hypothesis testing.

7.4.5 Model assumptions

For all methods outlined, underlying assumptions will be checked using standard methods, e.g. residual plots. If assumptions are not valid then alternative methods of analysis will be sought. If outlying observations are found which cause models not to fit the data adequately, such observations will be excluded from the main analyses and comments made in footnotes. Sensitivity analyses may be performed to examine the effect on the study's conclusions of excluding outlying observations.

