3.1 Sample size

The study sample size detailed in the protocol (version 6, 21 March 2012) is 2400 which corresponds to the entire predicted patient throughput at Bristol Heart Institute for the 2 year study period, allowing for up to 10% of patients to opt-out.

Details regarding the sample size calculation and review are given in the SAP covering analyses of pre-operative test results.

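### Section 7.4.5 makes exclusion of badly fitting observations the default for the main analyses, with no verified-error condition; judged by residuals, this can bias OR and AUC upward

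*SAP*

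**What the plan says.** Section 7.4.5 covers all the methods in the plan. It states that "underlying assumptions will be checked using standard methods, e.g. residual plots" and that other methods will be looked for if assumptions fail. It then sets the outlier rule: "If outlying observations are found which cause models not to fit the data adequately, such observations will be excluded from the main analyses", with a comment in a footnote. The last sentence reads: "Sensitivity analyses may be performed to examine the effect on the study's conclusions of excluding outlying observations".

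The section does not define an outlying observation, gives no cut-off, does not limit exclusion to confirmed errors, and does not say who decides or whether they can see the outcome.

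The rule reaches the main results. Under section 7.4.3, "The association between laboratory test results and outcome will be quantified using logistic regression for binary data", and "laboratory tests will be compared using the area under the receiver operating characteristic (ROC) curve". Sections 7.2 and 7.3 use such models to choose the best platform and to test whether adding another improves prediction.

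**The concern.** The study asks how well post-operative tests predict CCB. Patients whom a test predicts badly are part of the answer. A rule that removes observations because the model fits them badly selects the data by agreement with the model under test. Here the trimmed result is the headline, and a comparison with the full data is left to choice. A footnote discloses the exclusion but does not correct the estimate.

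The named diagnostic, the residual plot, depends on the outcome. In a logistic model with a minority outcome, the largest residuals belong to events with a low predicted risk, that is, CCB cases with a reassuring test result. Removing them makes the test look better than it is. If different patients are removed from the Multiplate, ROTEM and TEG models, each AUC is also computed on its own selected group.

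**Working it through.** The SAP states no figure on this point, so there is none to reproduce. The CCB rate is not given either (section 3.1 leaves the sample-size details to the pre-operative SAP), nor are an expected OR and an outlier cut-off. All three are assumptions below.

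**Who is flagged.** The Pearson residual is (y − p)/√(p(1 − p)). For an event it equals √((1 − p)/p), and for a non-event −√(p/(1 − p)). An absolute value above 2.5 therefore means:

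- events with p < 1/(1 + 2.5²) = 1/7.25 = 0.138;
- non-events with p > 1 − 0.138 = 0.862.

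**In terms of the test result.** Take logit p = a + 0.8x, with x standard normal and high values abnormal. Since ln(2.5²) = 1.833, events are flagged when x < (−1.833 − a)/0.8 and non-events when x > (1.833 − a)/0.8.

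| a | Event rate | Events flagged if | Non-events flagged if |
|---|---|---|---|
| −1.5 | 21% | x < −0.42 | x > 4.17 |
| −1.0 | 29% | x < −1.04 | x > 3.54 |
| −0.5 | 39% | x < −1.67 | x > 2.92 |

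Every flagged event lies on the normal side of the mean, and non-events are almost never reached.

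**Effect of dropping and refitting.** Integrating over x, with the model correct and no bad data:

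| Event rate | Dropped | Events among dropped | log-OR | AUC |
|---|---|---|---|---|
| 21% | 3.1% | >99.9% | 0.80 to 1.20 | 0.705 to 0.787 |
| 29% | 1.5% | 99.8% | 0.80 to 0.98 | 0.703 to 0.735 |
| 39% | 0.5% | 96% | 0.80 to 0.87 | 0.702 to 0.711 |

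At 21% events, the 3.1% of patients dropped are 3.1/20.9 = 15% of all CCB cases, and the OR per SD goes from e^0.80 = 2.23 to e^1.20 = 3.32. A cut of 3 drops about 1.3% and gives AUC 0.744. Simulations of 200,000 patients agree to within about 0.01 in AUC.

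**Other diagnostics.** Simulated studies of 2,000 patients (medians of 100, normal x unless stated):

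- 20% CCB, true OR 2, absolute deviance residual above 2: 3.0% dropped, all CCB cases; OR 2.02 to 2.95, AUC 0.685 to 0.767.
- 30% CCB, true OR 2, Cook's distance above 4/n: 3.8% dropped, 74% CCB cases; OR 1.99 to 3.02, AUC 0.679 to 0.744.
- 45% CCB, true OR 2, absolute Pearson residual above 2: 0.9% dropped, 85% CCB cases; OR 2.00 to 2.20, AUC 0.678 to 0.692.
- As the last, with a right-skewed test: 0.4% dropped, all non-cases; OR 2.04 to 2.19.
- 45% CCB, true OR 1.5, absolute Pearson residual above 2: almost nobody is flagged, and AUC stays at 0.611.

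**Extreme test values only.** With x beyond 3 SD dropped, the log-OR goes from 0.797 to 0.796 and AUC from 0.704 to 0.702. With a heavier-tailed test (t, 4 df), AUC goes from 0.686 to 0.676. There is no upward bias on this reading.

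**The case against.** The strongest objection is that the illustration applies a rule the SAP does not contain. Section 7.4.5 requires an observation to be outlying and also to spoil the fit. The illustration takes data that fit and drops everyone beyond a fixed cut. In 500 simulated studies of 2,000 patients at 21% events, a Hosmer-Lemeshow test rejected the fit in 5.8%, about the nominal rate, so on that test the trigger would rarely be met. This stands as a limit on the size. It does not rescue the rule: the SAP names residual plots, not a formal test, and leaves the judgement open. Where the rule is invoked on residuals, it selects by outcome.

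The plan also has safeguards: alternative methods in the same section, fractional polynomials in 7.3, paper-report and Lab Deviation checks in 4.2, and the footnote. None of them changes the default of exclusion.

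Three stronger readings are tempting, but the document does not support them.

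- That the rule does inflate OR and AUC. This depends on the meaning of outlying, the cut-off and the CCB rate, none of which is given.
- That the platform comparison is invalid. Section 7.4.5 does not say whether exclusions differ between platform models, and no platform comparison was simulated. The illustration also uses one predictor and omits the baseline score that 7.3 forces into the laboratory models.
- That bleeders are removed. Section 7.4.6 says many CCB cases had no excess drain loss or re-operation. The right term is CCB cases.

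**Conclusion.** The concern holds as a fault in the rule. Exclusion on fit is mandatory for the main analyses, the check on it is optional, and neither a confirmed error nor blinding to outcome is required.

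The direction is upward for OR and AUC if outliers are judged by residuals and CCB is a minority outcome. Under the assumed inputs, the AUC gain at a Pearson cut of 2.5 is about 0.08 at 21% events (0.787 − 0.705), 0.03 at 29% and 0.01 at 39%. The possible effect therefore runs from negligible to large, and this SAP cannot place the study within that range. If only extreme test values are removed, the OR does not move and AUC falls slightly.

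For the platforms, the supported statement is conditional: if the excluded patients differ between models, the AUCs are not compared like for like.

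**What to change.** Replace the outlier sentences in section 7.4.5 with a rule on these lines:

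- The main analysis keeps all valid observations.
- A value is excluded only if confirmed as a laboratory, data or linkage error through the checks in section 4.2, by someone who does not see the outcome.
- Poor fit is handled through functional form (the fractional polynomials of 7.3) or the alternative methods that 7.4.5 already allows.
- Any analysis without outlying observations is reported only as a sensitivity analysis, beside the full result, with the definition of outlying and the number of CCB cases and non-cases removed.
- Platforms are compared on the same set of patients.

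The cost is a few sentences in an SAP amendment. No new data are needed, and if models have already been fitted on trimmed data, they must be refitted.

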7.4.6 Sensitivity analyses

In order to aid understanding of the role of EPT within the definition of CCB, two post-hoc sensitivity analyses will be performed. This was decided in the light of a large proportion of patients classified as CCB having no excess bleeding (chest drain < 600 mL at 6 hours) and did not require a re-operation, but received pro-haemostatic treatments. Additionally, anecdotal evidence from consultant anaesthetists exists that a number of factors such as cardiac procedure are likely to affect their decision as to whether to administer these products.

The additional sensitivity analyses are as follows:

- Those defined as having received EPT but no observed chest drain > 600 mL by 6 hours post-operation, or re-operation for bleeding, will be excluded from the analyses and the models and ROC curves detailed in section 7 will be repeated.
- Those defined as having received EPT but no observed chest drain > 600 mL by 6 hours post-operation, or re-operation for bleeding, will be included in the analyses but reclassified as free from CCB.

7.4.7 Post-hoc sensitivity analyses

In recognition of the limitations of the EPT component of the primary outcome, a post-hoc approach was agreed where CCB would be defined as before, but those with those with

only 1 or 2 platelet transfusions, or with only 1 FFP transfusion would be excluded. Additionally those with >4 RBC units within 48hrs post-CICU admission would be included.

7.4.8 Missing data

In all tables missing data will be indicated by footnotes. If the amount of missing data differs substantially by outcome, the potential reasons will be explored.

Missing predictors or missing outcomes:

- If the proportion of missing data is less than 5% then complete case analysis will be performed (i.e. excluding cases with missing data).
- If the proportion of missing data is between 5% and 25%, marginal mean imputation will be performed. This involves imputing the most common category in the case of categorical data and the overall median or mean in the case of continuous data.
- If the proportion of missing data is above 25%, multiple imputation methods will be considered. A general imputation model that uses an iterative procedure to generate imputed values will be used to generate multiple complete data sets (e.g. using Stata's `mi impute`). The model of interest will be fitted to each of the complete data sets and effect estimates combined using Rubin's rules.

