⁶ These are: age, sex, diabetic status (n/y), cardiac procedure (CABG only, CABG + valve, valve alone, other), operative priority (elective, urgent), eGFR, preoperative HCT, treatment group, time since withdrawal (anti-platelet group), body mass index (BMI), preoperative platelet function and participation in another clinical study.

- Step 3 Test whether the addition of one of the other (post-operative) platforms improves this best model for **post-op CCB**. In practice, this is likely to be a test of whether Multiplate-post improves prediction compared to either ROTEM or TEG (or, adding ROTEM or TEG to Multiplate-post, since ROTEM and TEG are assessing similar mechanisms and Multiplate is assessing different ones). The combination of ROTEM and TEG together will not be considered.
- For the test/timepoint** added at Step 3 (assuming that there is one), we will also investigate whether a model using test variables that are available early (for the test/timepoint added at Step 3) performs as well as a model using the standard test variables available at “test completion.”
- Step 4 Test whether the addition of the pre-operative Multiplate platform improves the model identified in Stage 3.
- If Multiplate-pre** is added at Step 4, we will also investigate whether a model using test variables that are available early for Multiplate-pre performs as well as a model using the standard test variables available at “test completion.”

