7.3 Model fitting

Models will be fitted first for the standard time frame. Then, models will be fitted for the rapid time frame (see [Table 2.6.3](#)), testing whether this results in a “significant” deterioration in prediction. Comparing rapid and standard time frames is interesting because there may be a trade-off between potential benefits of earlier decision making (e.g. allows definitive treatment to be provided more quickly, thereby preventing blood loss) vs. potential harms (e.g. somewhat less good prediction).

The contribution of all of these baseline characteristics to the prediction of CCB were incorporated into a single score which was forced into models of laboratory predictors with a coefficient of 1.00 in order to enable comparisons between different models based on the various laboratory test platforms.

All laboratory measures from a platform were included for each model, with multivariable fractional polynomial techniques used to investigate the linearity of terms. All transformations and centering found to improve the fit of the models were implemented. Backward elimination was undertaken to select the final models with a threshold of inclusion of 0.05 and exclusion of 0.10. Initial models only considered the standard test results (see Table 2); subsequently the ‘early phase’ alternatives were considered for any terms that significantly contributed to the model.

The following models were constructed:

- **Model 2A:** pre-operative Multiplate in relation to **any CCB**
- **Model 2B:** pre-operative Multiplate in relation to **post-op CCB**
- **Model 2C:** post-operative Multiplate in relation to **post-op CCB**
- **Model 2D:** post-operative ROTEM in relation to **post-op CCB**
- **Model 2E:** post-operative TEG in relation to **post-op CCB**

Each model was then compared to a baseline model containing only the baseline characteristics in order to evaluate the contribution of the selected laboratory test results to the prediction of CCB. These are presented as receiver operating characteristic (ROC) curves.

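### The 5% complete-case limit in SAP 7.4.8 names no denominator; read per variable, it lets the platform models lose well over 5% of patients although no covariate exceeds the limit

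*SAP*

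**What the plan says.** SAP 7.4.8 sets three tiers under the heading "Missing predictors or missing outcomes".

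- Below 5%: "If the proportion of missing data is less than 5% then complete case analysis will be performed (i.e. excluding cases with missing data".
- From 5% to 25%: marginal mean imputation. "This involves imputing the most common category in the case of categorical data and the overall median or mean in the case of continuous data".
- Above 25%: multiple imputation is to be considered, for example with Stata's mi impute.

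No tier says what the proportion is a proportion of, and nothing limits the total share of patients a model may lose.

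Footnote 6 in 7.2 lists the baseline covariates. It begins with "age, sex, diabetic status (n/y), cardiac procedure (CABG only, CABG + valve, valve alone, other", continues with operative priority, and ends with "eGFR, preoperative HCT, treatment group, time since withdrawal (anti-platelet group), body mass index (BMI), preoperative platelet function and participation in another clinical study": 12 items in all. Section 7.3 then says: "The contribution of all of these baseline characteristics to the prediction of CCB were incorporated into a single score which was forced into models". The score enters each laboratory model with its coefficient fixed at 1.00.

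**The concern.** A patient with one missing, unimputed covariate has no baseline score and so drops out of every platform model, even with complete test results and a known outcome. Complete-case analysis below 5% is normally accepted because few patients are lost. A limit checked one variable at a time does not guarantee that when a model needs many variables together.

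The tiers also work against each other. A covariate just under the limit costs its incomplete patients, while one just over it is imputed and costs none, so more missing data can mean a larger analysis set.

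At stake are the precision of every platform model and the population that the results describe. Section 7.4.3 compares the tests by area under the ROC curve. That area, like a predicted risk, depends on which patients remain.

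**Working it through.** **Which reading.** The most common category, the median and the mean are properties of a single variable, so the middle tier can only be applied variable by variable. The lowest tier is the step below on the same scale. Per variable is therefore the natural reading, but it is not stated.

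**How many covariates could add to the loss.**

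- Footnote 6 lists 12.
- Section 6.4 merges treatment group, time since withdrawal and cardiac procedure into one variable, leaving 12 - 2 = 10 terms.
- Age, sex and trial participation are probably near complete (an assumption), leaving 7: diabetes, priority, eGFR, haematocrit, the merged variable, BMI and platelet function.
- eGFR and BMI both need weight (6.4), so they act partly as one source of gaps, giving about 6. If one more is near complete, 5 remain.

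Five or six is used below as an assumption.

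**Missing rates.** The document gives none, so a range from 2% to 4.9% is shown. There is no figure in the plan to reproduce.

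**Formulas.** With k covariates, each missing at rate m and with independent gaps, the share lost is 1 - (1 - m)^k. Standard errors then grow by about (1 - share lost)^(-1/2).

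| m | Lost, k = 5 | Lost, k = 6 | SE factor, k = 5 | SE factor, k = 6 |
|---|---|---|---|---|
| 2% | 1 - 0.98^5 = 9.6% | 1 - 0.98^6 = 11.4% | 1.05 | 1.06 |
| 3% | 1 - 0.97^5 = 14.1% | 1 - 0.97^6 = 16.7% | 1.08 | 1.10 |
| 4.9% | 1 - 0.951^5 = 22.2% | 1 - 0.951^6 = 26.0% | 1.13 | 1.16 |

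**What a one-fifth loss needs.** Solving 1 - (1 - m)^k = 0.20 gives m = 1 - 0.8^(1/k): 4.36% in each of five covariates, or 3.65% in each of six. Four covariates cannot reach it, since 1 - 0.951^4 = 18.2%.

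**Overlapping gaps.** Six covariates were simulated with equally correlated latent normal variables (400,000 draws):

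| Latent correlation | Lost at 2% each | Lost at 3% each | Lost at 4.9% each |
|---|---|---|---|
| 0.3 | 10.0% | 14.4% | 21.7% |
| 0.5 | 8.5% | 12.1% | 18.3% |
| 0.7 | 6.7% | 9.6% | 14.5% |
| 0.9 | 4.4% | 6.3% | 9.7% |

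If every gap falls in the same patients, the loss equals the single-variable rate, 2% to 4.9%.

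Missing laboratory results fall under the same rule and are not counted here.

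**The case against.** **The SAP may have meant a per-model proportion.** The lowest tier excludes cases, and the highest speaks of complete data sets and the model of interest. Read per model, the loss under the lowest tier is below 5% by definition. This reading is possible, but the middle tier does not fit it. Two analysts could also follow the text and fit different samples. The wording needs settling either way.

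**The exposed set is smaller than 12.** Sex and date of birth are linkage identifiers (4.1). Baseline creatinine falls back on the PATS value (4.2). Section 3.6 already restricts the data to patients with laboratory, CRF, PATS and INNOVIAN data. This stands, and is why the working uses five or six. A reader might multiply over all 12 and reach 45% at 4.9% each (1 - 0.951^12). That would need gaps in items such as age and sex, and it ignores the merging in 6.4.

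**Gaps cluster within patients.** This also stands. A reader might infer that a fifth or more of patients will be lost. The document gives no missing rates, so such a loss is possible near the limit but is not a forecast.

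**Bias does not follow automatically.** A reader might infer biased odds ratios because urgent patients have less complete records and, as 7.1 expects, more CCB. Operative priority is itself a model covariate, and complete-case logistic regression remains valid for adjusted odds ratios when missingness depends only on covariates in the model. Bias needs missingness related to CCB beyond those covariates, which nothing in the document shows.

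**Any threshold has a jump.** This is true, but here the jump runs the wrong way: patients are deleted on the side with less missing data.

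**Conclusion.** The concern holds as a possibility that the plan leaves uncontrolled. The 5% limit has no stated denominator. On its natural per-variable reading, the share of patients dropped from every platform model can be well above 5% while every covariate is within the limit.

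Under the assumption of five or six incomplete covariates with independent gaps, the loss runs from about 10% to 26% across the rates shown; overlap reduces it.

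The consequences are lower precision and a case mix that may no longer match the intended population for ROC areas and predicted risks. The document does not support a claim that the odds ratios are biased, or that a loss of any particular size will occur. The reversal at 5% is a fault of the per-variable rule whatever the missing rates. The change is worth making because it is cheap and decides who is analysed.

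**What to change.** Apply the limit per model. Suggested wording for 7.4.8:

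> Complete-case analysis will be used only if fewer than 5% of patients eligible for the model have any missing covariate in that model. Otherwise missing baseline covariates will be multiply imputed with the mi impute procedure of this section, in place of marginal mean imputation, with CCB and the test results in the imputation model. The number analysed will be reported for each model.

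Replacing marginal mean imputation for the covariates is deliberate. Once the limit is per model, several lightly incomplete covariates would otherwise be filled with a constant, which ignores their relation to the other variables and treats guesses as data.

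The cost is one paragraph of the SAP and some extra analysis, since the baseline score has to be formed in each imputed data set. The multiple imputation method is already named in 7.4.8. The downside is reliance on data being missing at random, which can do worse than complete cases if missingness depends on the unrecorded value itself.
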